4.4.6 Descriptive statistics for main intercurrent events

The number of participants with intercurrent event (ICE as defined in Section 8.3) 'use of systemic standard of care', with 'use of rescue medication', with 'discontinuation of study intervention due to lack of efficacy' and with 'discontinuation of study intervention due to other reasons' (i.e. not due to lack of efficacy) will be presented by treatment group and visit interval including cumulative numbers. Percentages will be calculated with respect to the number of participants in the analysis set.

The probability of the following events to occur during the treatment phase will be summarized for weekly intervals using the life table method:

- time to first use of rescue medication at or after Day 56 (Visit 6), first use of systemic SoC or discontinuation of study intervention due to lack of efficacy (all ICE as defined in Section 8.3), whatever comes first,
- time to first use of rescue medication at or after Day 1 (Visit 3), first use of systemic SoC or discontinuation of study intervention due to lack of efficacy (all ICE as defined in Section 8.3), whatever comes first,
- time to first use of systemic SoC or discontinuation of study intervention due to lack of efficacy (all ICE as defined in Section 8.3), whatever comes first.

The probability of an event to occur for the first time in the interval x_i to x_{i+1} will be calculated as follows:

Let

- $n_{x(i)}$ be the number of participants who had no such event until time x_i ,
- $r_{x(i)}$ be the number of participants with the first occurrence of such an event in the interval x_i to x_{i+1} ,
- $c_{x(i)}$ be the number of participants censored in the interval x_i to x_{i+1} Censoring will occur after early discontinuation of treatment due to other reasons (i.e. not lack of efficacy), after regular treatment completion and after use of rescue medication after the respective time point or use of SoC other than the intercurrent events defined in Section 8.3 (i.e. use not related to AD),
- $n'_{x(i)} = n_{x(i)} \frac{1}{2}c_{x(i)}$ be the effetive number of participants at risk for first occurrence of such an event in the interval x_i to x_{i+1} .

Then

• $p_{x(i)} = \frac{r_{x(i)}}{n'_{x(i)}}$ is the probability for first occurrence of such an event in the interval x_i to x_i given that no event occurred until time x_i

 x_{i+1} given that no event occurred until time x_i ,

• $P_{x(i)} = 1 - (1 - p_{x(0)})(1 - p_{x(1)}) \cdots (1 - p_{x(i)})$ is the probability for first occurrence of such an eventuntil time x_{i+1} .

Version 1.0

Page: 38 of 72

Time interval x to $x + \Delta x$ [weeks]	n _{x(i)}	r _{x(i)}	c _{x(i)}	n ' _{x(i)}	$1-p_{x(i)}$	p _{x(i)}	$1 - P_{x(i)}$	$P_{x(i)}$			
Zabedosertib											
0-1	100	2	0	100	0.98 (1-2/100)	0.02 (2/100)	0.98	0.020			
1-2	98	3	1	97.5	0.969 (1-3/97.5)	0.031 (3/97.5)	0.949	0.050			
2-3	94	5	2	93	0.946 (1-5/93)	0.054 (5/93)	0.898	0.101			
3-4	87	3	0	87	0.966 (1-3/87)	0.034 (3/87)	0.867	0.133			
11-12											
Placebo											

Table 4-3 Example for calculation of life table estimates

Note: Columns with gray text are for illustration purpose only and will not be presented in the outputs.

Furthermore, Kaplan-Meier curves for time of first occurrence of such an event will be presented by treatment group.

In addition, a graphical listing will be presented visualizing the time points of the visits and the intercurrent events as defined in Section 8.3 (use of rescue medication, use of SoC, early discontinuation of study intervention due to lack of efficacy) and the intercurrent event early discontinuation of study intervention due to other reasons not related to AD (not due to any ICE that is defined in Section 8.3) for each participant.

4.4.7 Pharmacokinetics

All PK analyses will be performed on the PKS.

Plasma samples will be collected for measurement of plasma concentrations of zabedosertib and its metabolite BAY 2822815 at Day 14 (Visit 4), Day 28 (Visit 5), Day 56 (Visit 6), Day 84 (Visit 7) pre-dose as well as between 0.5 to 1.5 hours and between 2 to 5 hours post-dose at Day 1 (Visit 3) and Day 84 (Visit 7).

The following statistics will be reported for plasma concentrations of zabedosertib and its metabolite at each visit (and time point if applicable): geometric mean, geometric standard deviation (re-transformed standard deviation of the logarithms) and geometric coefficient of variation (CV), arithmetic mean, standard deviation and CV, minimum, median, maximum value and the number of measurements as well as the number of measurements \geq limit of quantification (LLOQ). Means at any visit will only be calculated if at least 2/3 of the individual data were measured and were above LLOQ. Otherwise only minimum, median and maximum will be presented. For the calculation of the mean value, standard deviation and median a data point below LLOQ will be substituted by one half of this limit. In tables showing mean values, where values below LLOQ are included in the calculation of mean values, these means will be marked.

Furthermore, geometric means including one standard deviation range will be plotted for zabedosertib and its metabolite. The post-dose time between 0.5 to 1.5 hours post-dose will be presented at 1hour post-dose and the time between 2 to 5 hours will be presented at 3.5 hours post-dose on the x-axis.

Box plots including geometric mean for the concentration of zabedosertib and its metabolite BAY 2822815 will be presented as well.

Furthermore, individual plots of zabedosertib and its metabolite will be presented.

Pre-dose PK concentrations will be considered valid for inclusion into summary statistics if there were 8-16 hours between the last documented tablet intake before pre-dose PK sample collection and the pre-dose PK sample collection. Post-dose PK concentrations will be considered valid for inclusion into summary statistics if a tablet intake in the morning of the post-dose PK sample collection was documented. Furthermore, pharmacokinetic values might be flagged as invalid by the pharmacokinetic experts to be excluded from the calculation of summary statistics if applicable.

Zabedosertib is known to bind to alpha glycoprotein in plasma. Scatterplots of absolute concentration of alpha glycoprotein versus zabedosertib concentration in plasma (pre-dose) will be presented for Day 14 (Visit 4), Day 28 (Visit 5), Day 56 (Visit 6), Day 84 (Visit 7) in one plot (different symbols for the different visits will be used). Pearson and Spearman correlation coefficients will be given for the correlation over all visits combined.

4.4.8 Biomarkers

Post-dose biomarker samples will be considered as valid if no topical or systemic AD medication as defined in Section 8.3 (irrespectively of the indication) has been used within the last 7 days before the day of biomarker sample collection and if study intervention was not stopped earlier than 3 days before the day of biomarker sample collection.

Skin biopsy

Skin biopsy samples will be collected at Day 1 (Visit 3) and Day 84 (Visit 7, EOT) from a subgroup of participants willing to participate in this substudy. The analysis will be performed

with participants in the biomarker analysis set who participated in the biopsy substudy and have a biopsy at both visits.

The following assessments with the skin biopsy are optional (the list could be subject to change):

- Skin thickness (stratum corneum to stratum basale)
- Ki67 or MKI67 expression (no. of positively stained cells)
- CK16 or KRT16 expression (IRS score)

Summary statistics including absolute and percent changes to baseline will be presented for each assessment. A box plot will be presented showing the baseline and EOT assessments as well as the absolute change from baseline. Individual values will be plotted as well.

Biomarkers in blood

Blood samples for the inflammatory biomarker analysis will be collected at Day 1 (Visit 3) and Day 84 (Visit 7, EOT).

The analyses will be performed on the biomarker analysis set. Only participants with a blood sample at both visits will be considered.

The following inflammatory biomarkers will be analyzed (the list could be subject to change):

- TSLP (thymic stromal lymphopoietin),
- IL31 (Interleukin 31),
- IL33 (Interleukin 33),
- IL4 (Interleukin 4),
- IL13 (Interleukin 13),
- IL22 (Interleukin 22),
- CCL17 (C-C motif chemokine ligand 17).

Summary statistics including absolute changes to baseline will be presented for each inflammatory marker. Furthermore, summary statistics will also be presented for ratios to baseline using summary statistics as intended for log-normally distributed variables (geometric mean, SD and CV, minimum, median, maximum). For handling of inflammatory markers below the lower limit or above the upper limit of quantification refer to Section 4.1.1.

A box plot will be presented showing the baseline and EOT assessments as well as the ratio to baseline. Individual values will be plotted as well.

For each biomarker, an explorative ANCOVA will be performed with the log-transformed ratio-to-baseline at Day 84 (Visit 7) as dependent variable. The model will include treatment group as fixed effect and the log-transformed baseline concentration as covariate. Least square means will be calculated for each treatment group and two-sided 95% confidence intervals based on the t-distribution and the residual error of the model will be computed for the difference between treatment groups and back-transformed to the original scale.

4.5 Safety Analyses

All safety analyses will be performed on the SAF. Participants will be analyzed according to the treatment they actually received.

4.5.1 Extent of Exposure

Extent of exposure tables will be presented for the SAF, PPS and FAS.

Treatment duration will be defined as the number of days from the day of first study intervention intake up to and including the day of last study intervention intake excluding any gaps in study intervention intake (according to exposure data from eCRF) and will be summarized using descriptive statistics. In addition, the treatment duration will be categorized into weekly intervals (1-7 days, 8-14 days, 15-21 days, ..., 78-84 days, > 84 days) and the frequency of participants per interval will be summarized.

The total treatment dose (according to drug accountability data from eCRF) will be summarized in milligram using descriptive statistics. In addition, the treatment dose will be categorized into groups of 2000 mg (0 - 2000 mg, >2000 - 4000 mg etc.) and the frequency of participants per group will be summarized.

The treatment compliance will be calculated between start and end of treatment as the number of tablets actually taken divided by the number of planned tablets multiplied by 100 with:

• Number of tablets actually taken (based on drug accountability data): no. of tablets dispensed – no. of tablets returned – no. of tablets lost

In case of unreturned study drug intervention bottles study drug intake documentation from the hand-held device on daily basis will be used to replace the missing drug accountability data unless further information is provided by the participant (and documented via number of lost tablets). Otherwise, if no further information is available and no replacement is possible from diary data it will be assumed that no tablets have been taken.

• Number of planned tablets:

The number of planned tablets will be calculated based on the planned dose of 2 tablets per day for each day starting with first intake of study intervention to the last intake of study intervention. For the first and last day of study intervention intake only one planned tablet will be considered if the time of first intake is after 3 pm or the time of last intake is before 3 pm (if no time is available the default will be two doses on the first day of study intervention intake and one dose on the last day). The compliance will be summarized descriptively. In addition, the compliance will be categorized into three groups of <80%, 80-120%, and >120% and the frequency of participants per group will be summarized.

In addition, the following compliance calculations will be needed to check validity for the PPS: treatment compliance will be calculated and summarized presenting the percent of tablets actually taken with respect to the planned number of tablets

a) between start of treatment and end of treatment or start of rescue medication (irrespectively of indication) at or after Day 56 (Visit 6), whatever comes first,

b) during the last 4 weeks before end of treatment or start of rescue medication (irrespectively of indication) at or after Day 56 (Visit 6), whatever comes first.

Compliance calculations as follows will be needed to check for validity for the BAS: treatment compliance will be calculated and listed presenting the percent of tablets actually taken with respect to the planned number of tablets

c) during the last 4 weeks before end of treatment.

Study intervention intake documented by the participant on the hand-held device on daily basis will be used to calculate the number of tablets actually taken for a)-c). If the documentation in the diary has gaps (e. g. due to technical reasons or if the end date documented in the eCRF is more than one day after the last study drug intake documented in the diary) this information will be replaced by drug accountability data, if possible. If data from the diary is replaced by drug accountability data complete intervals of drug accountability data will be used, i. e. between dispense and return date of the medication or treatment end date if medication returned later (in case of bottles returned after dispensation of the next kit overlapping drug accountability data will be combined). If drug accountability intervals don't fit the required interval diary data will be considered to subtract the tablets taken on the extra days if possible (i. e. if the respective diary records are available). If not possible the diary data will be used as is.

In case of unresolved discrepancies between study intervention intake documented in the participant hand-held device and the study intervention intake assessed by counting returned tablets it will be discussed during blind data review if the study intervention intake documentation is considered reliable.

Frequencies of participants with study intervention interruptions will be presented overall and by reason for the interruption and duration of study intervention interruption.

4.5.2 Adverse Events

The secondary safety endpoint is the frequency and severity of TEAEs.

Any AEs related to study procedures recorded after signing of informed consent but prior to first treatment with study intervention will be considered as pre-treatment AEs. *TEAEs are events that start after the first treatment with the study intervention and until 7 days after the last intake of study intervention*. AEs that occurred 8 days after last dose or later will be considered as post-treatment AEs.

All TEAEs will be listed.

Individual listings of all AEs will be provided indicating whether the AE is treatment emergent and including AE onset and end date relative to start and end date of treatment and the duration of the AE.

The following AEs have been defined as AEs of special interest and are recorded as such:

- Confirmed or suspected severe invasive bacterial infections,
- Systemic hypersensitivity reactions,
- Non-invasive infections (skin),
- Unexplained cases of rhabdomyolysis.

Adverse events will be coded using medical dictionary for regulatory activities (MedDRA) terms using the most recent effective MedDRA version as per TS domain.

Overall summaries of the number of participants with any AEs, pre-treatment AEs, TEAEs, and post-treatment AEs will be presented. The overall summary will comprise the frequency of participants with certain AEs: Participants with

- any AE,
- any AE by maximum intensity (mild, moderate, severe),
- any AE related to study drug,
- any AE related to study drug by maximum intensity (mild, moderate, severe),
- any AE related to study procedures,
- any AE leading to discontinuation of study drug,
- any AE of special interest (also broken down by category of special interest as stated above),
- any SAE,
- any SAE related to study drug (maximum intensity),
- any SAE related to study procedures,
- any SAE leading to discontinuation of study drug,
- any AE with outcome death.

The frequency of participants with

- SAEs
- TEAEs,
- TEAEs by maximum intensity,
- TEAEs related to study drug,
- TEAEs related to study drug by maximum intensity,
- TEAE of special interest,
- TEAE of special interest by maximum intensity,
- TEAEs of special interest related to study drug,
- TEAEs resulting in discontinuation of study drug,
- TEAEs resulting in discontinuation of study drug by maximum intensity,
- TEAEs resulting in discontinuation of study drug and related to study drug,
- serious TEAEs,
- pre-treatment AEs,
- post-treatment AEs

will be summarized using the MedDRA terms system organ class (SOC) and preferred term (PT).

In case of events with different intensity within a participant, the maximum reported intensity will be used. If intensity is missing, the event will be considered as severe. If the same event is reported as both unrelated and related to the study intervention within a participant, the event will be considered as related to study intervention. If the study intervention relationship is missing, the event will be considered as being related to the study intervention.

Death, TESAEs, TEAESIs or TEAEs leading to discontinuation of study intervention, TEAEs not resolved at end of study *will be listed separately.*

Additionally, a listing of participants with COVID-19 adverse event will be presented (with COVID-19 AEs only and another listing with all AEs of participants with COVID-19 AE).

4.5.3 Additional Safety Assessments (if applicable)

Laboratory assessments

Continuous laboratory values will be summarized descriptively by parameter including changes from baseline. Arithmetic mean plots including standard deviation over time will be presented (LLN and ULN will be indicated if applicable, in case of multiple normal ranges, the lowest LLN and highest ULN will be presented). For laboratory parameters with multiple normal ranges the summary statistics will also be broken down by normal range. In addition, the lab values will be presented for the normalized values. Normalization will be performed as follows: (value – LLN)/(ULN – LLN). In addition, box plots including arithmetic means over time will be presented for changes from baseline. Individual plots of laboratory values will also be presented (in case of multiple normal ranges).

For the laboratory parameters aspartate aminotransferase (AST/SGOT), alanine aminotransferase (ALT/SGPT), creatine kinase, high sensitivity C reactive protein (hsCRP) concentration, as well as white blood cell, neutrophil and lymphocyte counts, a proc mixed repeated measurement model will be calculated with the change from baseline at all post-dose visits as dependent variable. The model will include treatment group, visit and the interaction of visit and treatment group (visit*treatment group) as fixed effects and the respective baseline concentration as covariate. The covariance structure for the within-subject correlation between outcomes at different timepoints will be assumed to be unstructured. The structure of the covariance matrix might be adapted, e. g. in case of convergence problems. Least square means will be calculated for each treatment group and two-sided 95% confidence intervals based on the t-distribution and the residual error of the model will be computed for the difference in treatment means.

The number of participants with treatment-emergent high (>ULN) or low (<LLN) abnormal laboratory values will be summarized for each laboratory parameter.

In addition, hepatocellular drug-induced liver injury screening plots will be provided as decribed in the FDA standard safety tables and figures: integrated guide document. The hepatocellular drug-induced liver injury screening plot will present each participant based on their maximum post-baseline total bilirubin (y-axis) and transaminase (ALT or AST, whichever is higher). Each value is expressed as multiples of the ULN. Dashed lines in this

plot represent total bilirubin and transaminase cutoffs of 2 x ULN and 3 x ULN, respectively and are based on Hy's Law criteria. Potential Hy's Law cases will be circled red and are defined as having any post-baseline total bilirubin equal to or exceeding 2 x ULN within 30 days after a post-baseline ALT or AST equal to or exceeding 3 x ULN, and maximum postbaseline ALP <2 x ULN. Furthermore, a cholestatic drug-induced liver injury screening plot will present each participant by their maximum ALP versus their maximum total bilirubin values in the post-baseline period. A potential cholestatic drug-induced liver injury case (red circled) will be circled red and is defined as having a maximum post-baseline total bilirubin equal to or exceeding 2 x ULN within 30 days after post-baseline ALP became equal to or exceeding 2 x ULN.*For laboratory values shift tables will be provided (by time point including any time point* during treatment phase) *focusing on the frequency and percentage of participants with shifts from within normal range (or below normal range) at baseline to above normal range post-baseline and from within normal range (or above normal range) at baseline to below normal range post-baseline*.

Frequency tables will be provided for semi-quantitative and qualitative data.

Courses of abnormal laboratory values (continuous and qualitative data) at least at one visit will be listed by parameter as absolute values and – if applicable – as multiples of the respective upper or lower limit (abnormal values will be flagged with 'H' for high and 'L' for low).

Furthermore, a frequency table with the number of subjects with the following treatmentemergent laboratory abnormalities will be presented. A laboratory abnormality is considered to be treatment-emergent if it occurs after treatment start and up to 7 days after end of treatment and has not been present before treatment start. The following abnormalities will be considered:

Laboratory abnormalities leading to study drug discontinuation:

- WBC count < 1000 cells/ μ L; < 1.0 x 10⁹/L,
- Absolute neutrophil count < 500 cells/ μ L; < 0.5 x 10⁹/L,
- Lymphocyte count $< 200 \text{ cells}/\mu\text{L}; < 0.2 \text{ x } 10^9 /\text{L},$
- Hemoglobin < 8 g/dL,
- Creatine kinase (CK) > 10 x ULN

Liver abnormalities:

- ALT or $AST > 3 \times ULN$
- ALT or AST > 3 x ULN and total bilirubin (TBL) > 2 x ULN
- ALT or AST > 3 x ULN and INR > 1.5 x ULN (INR > 1.5 x ULN is only relevant if the participant is not on Vitamin K antagonist, new oral anticoagulants (NOACs) or heparin.)
- ALT or $AST > 5 \times ULN$ for more than 2 weeks
- ALT or $AST > 8 \times ULN$

Abnormalities with respect to neutrophil counts:

- Absolute neutrophil count < 500 cells/ μ L,
- Absolute neutrophil count 500 to < 1000 cells/ μ L,
- Absolute neutrophil count 1000 to < 1500 cells/ μ L.

Abnormalities with respect to creatinine kinase:

- Creatine kinase (CK) >ULN to < 5 x ULN,
- Creatine kinase (CK) 5 to 10 x ULN,
- Creatine kinase (CK) > 10 x ULN.

Vital signs

Vital signs will consist of single measurements of systolic blood pressure, diastolic blood pressure, pulse rate and body temperature. Vital signs including height (only summary statistics for the baseline value), weight and BMI will be summarized descriptively by parameter including absolute changes from baseline. Arithmetic mean plots including standard deviation over time will be presented. In addition, box plots including arithmetic means over time will be presented for changes from baseline. Individual plots over time will be generated.

Electrocardiogram

Single 12-lead ECG will be obtained locally.

ECG parameters (PR, QRS, QT, corrected QT intervals (according to Bazett's formula) and the ventricular rate) will be summarized descriptively by parameter including absolute changes from baseline. Arithmetic mean plots including standard deviation over time will be presented. In addition, box plots including arithmetic means over time will be presented for changes from baseline. Individual plots over time will be presented.

Furthermore, frequency tables will be presented for corrected QT intervals for absolute values with the following categories:

• >450 to 480 msec, >480 msec to 500 ms, >500 msec,

and absolute change from baseline with the following categories:

• >30 to 60 msec, >60 msec.

A frequency table will be provided for the ECG findings assessed by the investigator, and for overall interpretation of ECGs (normal; abnormal, clinically insignificant; abnormal, clinically significant).

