7.1.2 QTc Stopping Criteria

If a clinically significant finding is identified (including, but not limited to changes from baseline in QT interval corrected using Bazett's formula [QTcB] after enrollment), the investigator or qualified designee will determine if the participant can continue in the study and if any change in participant management is needed. A review of the ECG at the time of collection must be documented. Any new clinically relevant finding should be reported as an AE.

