8.3.3 Electrocardiograms

Single 12-lead ECG will be obtained as outlined in the SoA (see Section 1.3) or as clinically indicated using an ECG machine that automatically measures the ECG mean ventricular rate, PR, QRS, QT, and QTc intervals. Refer to Section 7.1.2 for QTcB withdrawal criteria and any additional QTcB readings that may be necessary.

ECG for each participant should be obtained using the same electrocardiograph machine whenever possible. To minimize variability, participants should remain in a resting position for at least 5-10 minutes prior to each ECG recording.

Quality of ECGs should be assessed immediately and in case of improper quality of an ECG another ECG(s) should be recorded to replace the improper ECGs, which would be documented as invalid by the investigator.

For each ECG, the investigator has to perform a thorough review that may result in ECG findings and an overall assessment (including clinical relevance) deviating from the automated device output.

Each ECG will be evaluated for the overall normality as follows:

- Normal
- Abnormal, clinically insignificant
- Abnormal, clinically significant.

Only the results of this local review will be entered as findings into the electronic CRF and any clinically relevant abnormality should be documented as an AE or SAE. ECG findings observed before first study intervention intake that reflects any previous cardiovascular

disease (e.g., atrial fibrillation, previous myocardial infarction or any abnormality in the electrical conduction system) should be documented as medical history.

ECG recordings will be kept as part of subjects file at the site as per site practice.

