8.4.6 Cardiovascular and Death Events

BAY 1834845 and its metabolite M-5 (BAY 2822815) did not show activity at potential offtargets and did not interact with cardiac ion channels (human ether-à-go-go-related gene [hERG], human sodium channel/current isoform 1.5 [hNav1.5], and human calcium channel/current isoform 1.2 [hCav1.2]).

In-vivo, BAY 1834845 was devoid of acute adverse effects on vital organ functions in rats (central nervous and respiratory system), and in both Beagle dogs and Cynomolgus monkeys (hemodynamic and electrocardiogram parameters).

In the FiM study (18384), no TEAEs were reported relating to changes in vital sign values nor to cardiac-related symptoms following treatment with zabedosertib.

In the drug interaction study (18387, Part B), one subject had documented palpitations; there were no subjects with clinically significant ECG findings, and no further TEAEs were reported relating to changes in ECG values following treatment with zabedosertib.

In the multiple dose study (18385), one subject had documented palpitations; there were no subjects with clinically significant ECG findings, and no further TEAEs were reported relating to changes in ECG values following treatment with zabedosertib. No new safety findings related to cardiovascular and death events were identified from Study 21329.

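### QTc is corrected with Bazett's formula only, which leaves a heart-rate-dependent bias in the descriptive QTc summaries and category tables

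*SAP*

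**What the plan says.** SAP 4.5.3 (Electrocardiogram) states: "ECG parameters (PR, QRS, QT, corrected QT intervals (according to Bazett's formula) and the ventricular rate) will be summarized descriptively by parameter". Changes from baseline, mean plots, box plots and individual plots go with these summaries.

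It then adds two sets of counts. For the first, "frequency tables will be presented for corrected QT intervals for absolute values with the following categories": above 450 to 480, above 480 to 500, and above 500 msec. The second set covers change from baseline: ">30 to 60 msec, >60 msec". The phrase "corrected QT intervals (according to Bazett's formula" is the only place where a correction is defined, so both sets use QTcB.

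Protocol 7.1.2 also refers to "changes from baseline in QT interval corrected using Bazett's formula [QTcB] after enrollment". Protocol 8.3.3 requires a machine that "automatically measures the ECG mean ventricular rate, PR, QRS, QT, and QTc intervals", so the inputs for another correction are measured on every ECG. The SAP also says: "Single 12-lead ECG will be obtained locally".

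The Schedule of Activities marks ECGs at Visits 1, 4, 7 and 8. Under the baseline rule in SAP 4.1.1, the baseline ECG is therefore normally the single screening recording, taken 14 to 28 days before Day 1.

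**The concern.** Bazett divides QT by the square root of RR. If QT varies less steeply with RR than that, QTcB rises when heart rate rises and falls when it falls, even though repolarisation has not changed. A participant's category can then reflect heart rate rather than QT.

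The change tables count increases only, so a rate rise can add entries and a rate fall can remove them. The absolute table is affected even without a change on treatment, because a fast resting rate inflates QTcB at every visit.

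The planned arms are 48 and 24 participants. One reclassified participant moves a percentage by 1/48 = 2.1 points on zabedosertib or 1/24 = 4.2 points on placebo. Change in ECG parameters is a listed safety endpoint (Protocol 3.1), so these tables will be read.

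**Working it through.** The plan gives no QTc figure to reproduce.

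**Inputs from the documents:** Bazett correction, the category limits, and availability of QT and ventricular rate.

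**Assumptions, none of them in the documents:** QT proportional to the cube root of RR; rate-independent QTc of 380–440 msec; baseline rate of 60–80 beats/min. A linear relation, QT = QTc − 154 × (1 − RR) with RR in seconds and QTc of 400–420 msec, serves as a variant.

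**Formula.** With RR = 60/HR and QT = QTcF × RR^(1/3), QTcB = QT/RR^(1/2) = QTcF × (HR/60)^(1/6).

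**1. Shift from rate alone, QTcF held at 400 msec.**
- 65 beats/min: 400 × (65/60)^(1/6) = 405.4
- 85 beats/min: 400 × (85/60)^(1/6) = 423.9, a shift of about +18.5 msec
- 95 beats/min: 400 × (95/60)^(1/6) = 431.8, a shift of about +26 msec

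Neither shift reaches 30 msec.

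**2. Rise needed to cross a limit c by rate alone.** The required rate ratio is ((QTcB0 + c)/QTcB0)^6. From QTcB0 = 400 at 60 beats/min:
- c = 30: (430/400)^6 = 1.543, so 60 to 93 beats/min (+33)
- c = 60: (460/400)^6 = 2.313, so 60 to 139 beats/min (+79)

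| Relation | Rise for >30 msec | Rise for >60 msec |
|---|---|---|
| Cube root, QTc 380–440, 60–80 beats/min | 29–44 | 69–106 |
| Linear, QTc 400–420, 60–80 beats/min | 27–33 | 54–63 |

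**3. Borderline participants.** A rise of 10 beats/min adds about 8 to 11.5 msec across both relations. Take a uniform +10 msec and a normally distributed change with an assumed within-person SD:

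| SD (msec) | P(change >30), no shift | P(change >30), +10 msec | P(change >60), +10 msec |
|---|---|---|---|
| 10 | 0.1% | 2.3% | <0.1% |
| 15 | 2.3% | 9.1% | <0.1% |
| 20 | 6.7% | 15.9% | 0.6% |

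A single case shows the same thing. A true +20 msec (400 to 420) with 65 to 75 beats/min gives 420 × (75/60)^(1/6) − 405.4 = 435.9 − 405.4 = +30.5 msec, which is counted.

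**4. Masking.** A true +35 msec (400 to 435) with a fall from 80 to 65 beats/min gives 435 × (65/60)^(1/6) − 400 × (80/60)^(1/6) = 440.8 − 419.6 = about +21 msec, which is not counted.

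**5. Absolute table.** QTcB passes 450 msec when HR = 60 × (450/QTcF)^6.
- QTcF 430: 60 × 1.314 = about 79 beats/min
- QTcF 440: 60 × 1.144 = about 69 beats/min

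**6. With QTcF tabulated.** Under the cube-root assumption the artefact is 0 msec at every rate.

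**The case against.** **The SAP follows the protocol, and these tables decide nothing.** Both documents name Bazett, so there is no contradiction. ECG change sits among the other safety endpoints of a Phase 2a proof-of-concept study, and the tables are descriptive. This stands, and it limits the weight of the point.

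**The artefact would be visible.** Uncorrected QT, ventricular rate and pulse rate are summarised with changes from baseline. Placebo is concurrent, and Protocol 8.3.3 asks for 5 to 10 minutes' rest before each ECG. This stands at group level: a rate shift on drug would show. It does not reassign any individual in the QTc categories.

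**The cube-root relation makes Bazett wrong by construction.** This is fair. The linear variant gives similar sizes (a rise of 20 beats/min adds about 17 to 22 msec, against 15 to 22 under the cube root), but the true relation in these patients is unknown. That argues for showing both corrections.

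**Two stronger readings are tempting and not supported.**
- A reader might infer that any heart-rate change on drug will appear as a false entry above 30 or 60 msec. Steps 1 and 2 show otherwise, and a fall in rate cannot create an entry in tables that count increases only.
- A reader might take the palpitations in Protocol 8.4.6 as evidence of a rate effect. For each of two earlier studies it says "one subject had documented palpitations", but the same sentences report no clinically significant ECG findings. The section also reports no vital-sign or cardiac-symptom events in the first-in-man study and no interaction with the cardiac ion channels tested. The palpitations carry no weight here.

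**Conclusion.** The point holds in a limited form. Using Bazett alone leaves a rate-dependent bias of about 18.5 msec for a rise from 65 to 85 beats/min at a cube-root QTc of 400 msec. Rate alone should rarely fill the category above 30 msec and almost never the one above 60 msec. The realistic effects are extra borderline entries above 30 msec, masking when rate falls, and entries above 450 msec at ordinary resting rates.

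All sizes depend on the assumed QT–RR relation, baseline QTc, heart rate and within-person SD. The bias between arms is conditional: it needs a rate shift that differs by arm, and the documents establish none. Shifts common to both arms add noise to the counts. The primary endpoint and the posterior-probability rule are unaffected. This is a worthwhile improvement of low severity.

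**What to change.** In SAP 4.5.3, define QTcF = QT/RR^(1/3), with RR = 60/ventricular rate in seconds, derived for each ECG from the recorded QT and ventricular rate. Present the descriptive summary, the absolute-category table and the change-category table for QTcF beside the existing QTcB versions. Keep the QTcB outputs, because Protocol 7.1.2 refers to that measure, and leave 7.1.2 unchanged.

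The cost is one derived variable and a repeat of existing tables. No new data, visits or procedures are needed. With two corrections, some participants may fall in different categories, so a footnote should state both formulas.
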